**4. Design and Procedures:** This will be an unblinded, open-label study enrolling patients who are scheduled to undergo thoracic radiation therapy as part of their standard clinical care as well as healthy volunteers. Approximately 35 subjects will be consented including screen fails. Subjects to be enrolled will include males and females over 18 years old, for a targeted enrollment of 20 subjects undergoing RT. An additional 10 healthy volunteers will be enrolled to optimize the MRI parameters and provide reference images for normal pulmonary function. After consent and screening, healthy volunteers will undergo just one study visit. Patients scheduled for RT will be seen up to 2 time points after consent and screening with an optional 3rd time point— a baseline Visit 1 (before RT begins), Visit 2 (at ten-fourteen weeks post RT) and optional visit 3 (thiry-two to forty weeks post RT). For patients who participate in 2 visits, their participation will last until approximately 4 months after RT is completed, while patients completing the optional 3rd visit will participate until 12 months after RT. At each visit, subjects will undergo pulmonary function testing and MRI. The objective of the MRI session is to acquire 3D images of pulmonary structure, ventilation, gas exchange and perfusion. Each session should take approximately 3 hours of the subject's time.

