
1. Patient scheduled to undergo thoracic RT at Duke University to a dose of at least 20 Gy
2. Willing and able to give informed consent and adhere to visit/protocol schedules

Exclusion Criteria:

1. Subject is less than 18 years old
2. MRI is contraindicated based on responses to MRI Screening questionnaire
3. Subject is pregnant or lactating
4. Respiratory illness of a bacterial or viral etiology within 30 days of MRI
5. Subject has any form of known cardiac arrhythmia
6. Subject does not fit into  $^{129}\text{Xe}$  vest coil used for MRI
7. Subject cannot hold his/her breath for 15 seconds
8. Subject deemed unlikely to be able to comply with instructions during imaging
9. Medical or psychological conditions which, in the opinion of the investigator, might create undue risk to the subject or interfere with the subject's ability to comply with the protocol requirements.

Inclusion/Exclusion Criteria for Healthy Volunteers

1. Subject meets all criteria above but does not have a clinical diagnosis of respiratory disease.

Subject Identification: Upon providing consent, the subject will be assigned a subject identification number (SIN), which will be used for all data collection and imaging studies. The SIN will consist of a study identifier and four digit extension (e.g. -0001 for the first subject).

**6. Subject Recruitment and Compensation:** Healthy volunteers as well as patients who will be undergoing thoracic radiation therapy will be recruited via flyers and website postings. Patients scheduled to undergo thoracic radiation at Duke University may also be informed about study participation by their physician or physician's staff. If they are interested in participating and appear to meet all inclusion criteria they will be referred to the study coordinator for formal consenting. It is expected that up to 10 healthy volunteers and 25 patients scheduled for RT will

be recruited in this first phase of the study. Recruitment will be open to all demographic groups. Subjects will be compensated after each study visit for their travel/parking and time. If a procedure has to be cancelled for technical reasons after a subject has arrived on site, the subject will be compensated as though he/she had completed the study. The subject will be encouraged, but not required to return at a later date to complete the procedure. If the subject returns, he/she will be compensated again.

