We plan to enroll a total of 25 patients who undergo radiation therapy. Taking 20% attrition rate into account, the study will have a total of 20 treated patients who have  $VDP$  measures at both baseline and Visit 2 (at 10-14 weeks post RT). With valid  $VDP$  measures from 20 patients, the study has approximately 81% power to detect a 12% increase in  $VDP$  after RT at Visit 2 relative to baseline. This calculation assumes a one-sided significance level of 0.05 using a Wilcoxon Signed-Rank Test. These results are based on 2000 Monte Carlo samples and the assumption that the paired  $VDP$  measures follow a bivariate normal distribution with standard deviation 16 and correlation 0.2.

In addition to  $VDP$ , pulmonary functional images pre- and post RT will also be evaluated using the EDP and PDP metrics described above, as well as the regional differences in  $^{129}\text{Xe}$  uptake in barrier tissues vs RBCs. Functional imaging maps will be co-registered with the patient's dose plan. Functional metrics such as RBC:barrier ratio will be computed in isodose regions and correlation plots will be generated.

The mean, standard deviation, median and range of  $VDP$  and other pulmonary function measures and the changes relative to baseline will be estimated for each visit at which MRI imaging is undertaken. The 95% confidence interval for means and averaged changes relative to baseline will be provided. The  $VDP$  increase 6 weeks after radiation therapy compared to baseline will be tested using Wilcoxon Singed-Rank test. To control overall type I error, formal hypothesis testing will not be conducted for the secondary endpoints for pulmonary functions. The trajectory changes of these endpoints over time and the dose-dependent damage effect will be evaluated using linear models for repeated measures. Point estimates and confidence intervals for relevant parameters will be provided for descriptive purpose. Appropriate transformation will be taken on these endpoints if normality assumption is clearly violated in the regression analysis.

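### Section 4 gives 20 RT patients as the enrolment target, but in Section 12 that number is what remains of 25 enrolled after 20% attrition

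*Combined protocol and SAP*

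**What the plan says.** Three sections of the combined protocol and SAP give patient numbers.

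- **Section 4 (Design and Procedures)** sets the RT group "for a targeted enrollment of 20 subjects undergoing RT". It adds: "An additional 10 healthy volunteers will be enrolled to optimize the MRI parameters". For the overall total it states: "Approximately 35 subjects will be consented including screen fails".
- **Section 6 (Subject Recruitment and Compensation)** expects "up to 10 healthy volunteers and 25 patients scheduled for RT" to be recruited.
- **Section 12 (Data Analysis & Statistical Considerations)** states: "We plan to enroll a total of 25 patients who undergo radiation therapy". It continues: "Taking 20% attrition rate into account, the study will have a total of 20 treated patients", meaning patients with VDP at baseline and at Visit 2. With those 20, "the study has approximately 81% power to detect a 12% increase" in VDP, using a one-sided Wilcoxon signed-rank test at the 0.05 level.

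Section 12 does not define attrition. In particular, it does not say whether screen failures count towards the 20%.

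**The concern.** Sections 4 and 12 both speak of enrolling RT patients and give different numbers. Section 12 shows where 20 comes from: it is the number left with paired measurements once losses are deducted. Section 4 gives the same number as the target for entry.

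The stated power depends on 20 complete pairs, and VDP is the only endpoint to be formally tested. Section 4 is the design section, so staff could take its 20 as the point at which to close enrolment. Section 13 makes the principal investigator responsible for preventing over-accrual and addressing under-accrual, but gives no number. Under Section 4, patients 21 to 25 could be counted as over-accrual; under Section 12, stopping at 20 is under-accrual.

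The consent total adds a second ambiguity. Section 4 leaves a margin of about five that appears to be for screen failures. Section 12 also has a margin of five, but assigns it to attrition.

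**Working it through.** **Inputs.** From Section 12: 25 RT patients enrolled, 20% attrition, 12% increase in VDP, SD 16 at each time, correlation 0.2, one-sided 0.05 signed-rank test, 2000 simulated samples. From Section 4: 20 RT patients, 10 volunteers, about 35 consents. The 12% is read as 12 VDP points, which is an assumption; this reading reproduces the stated power.

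**Counts.**
- Section 12: 25 × (1 − 0.20) = 20, and in reverse 20 / 0.80 = 25. The section is internally consistent.
- Section 4's 20 taken as enrolled: 20 × (1 − 0.20) = 16 pairs.
- Section 4 total: 20 + 10 = 30, leaving 35 − 30 = 5.
- With 25 enrolled: 25 + 10 = 35, leaving 35 − 35 = 0 for screen failures.

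**The plan's own power figure.**
- SD of change = √(2 × 16² × (1 − 0.2)) = 20.24.
- Standardised effect = 12 / 20.24 = 0.593.
- Exact one-sided signed-rank test, 20 pairs, 400,000 simulated replicates: power 0.799 (attained alpha 0.0487).
- Standard error of a 2000-sample simulation = √(0.8 × 0.2 / 2000) = 0.009. The stated 0.81 differs from 0.799 by 0.011, which is compatible with simulation error.

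**Power if only 20 are enrolled.** The same calculation at 16 pairs gives 0.703 (attained alpha 0.0467). With the normal approximation to the test, a separate 20,000-replicate simulation gives about 0.72 at 16 pairs.

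**Attrition as a random quantity.** Let the number of pairs be Binomial(N, 0.8), with independent losses, and average power over it:

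| RT patients enrolled | Expected pairs | Average power | Chance of at least 20 pairs |
|---|---|---|---|
| 25 | 20 | 0.796 | 0.617 |
| 20 | 16 | 0.703 | 0.8²⁰ = 0.012 |

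Allowing for random losses does not change the comparison.

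**The case against.** The strongest reply is that Section 4 separates consent from enrolment. On that reading, 25 RT patients are consented, about five fail screening and 20 are enrolled. Then 25 + 10 = 35 matches the consent total, and Section 6, which speaks of recruitment, agrees with Section 4. The Schedule of Events puts screening and Visit 1 on the same day for most subjects, so a single loss figure counted from consent is possible. The conflict would then come down to the verb used in Section 12. The reply adds that no calculation in the plan is wrong, and that the fall to 70% needs staff to stop at 20 despite Section 12.

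Much of this stands. Section 6 alone does not contradict Section 4. The fault is inconsistent labelling of a sample size, not a faulty calculation, and the loss of power is conditional. The 62% and 1% chances also assume independent losses, which the documents do not state.

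The reconciliation still fails against Section 12, which enrols 25 and attributes the fall to 20 to attrition. If five patients are used up at screening, none is left to cover losses between baseline and Visit 2, at 10 to 14 weeks after RT. The same five places can serve both purposes only if attrition is defined to include screen failures, and the protocol does not say so.

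**Conclusion.** The point holds: Section 4 is wrong as written, because it gives Section 12's post-attrition count as the enrolment target. The power calculation is not in dispute.

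If accrual follows Section 12, or if Section 4's 20 means patients with paired VDP, the effect on power is nil. If accrual stops at 20 enrolled, power falls from about 80% to about 70%. That loss of about 10 points rests on the plan's own 20% attrition and variance assumptions and on reading the increase as 12 VDP points. The correction should be made because this number sets the size of the only formal test.

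**What to change.** 1. Decide whether the 20% attrition covers screen failures, and say so in one sentence in Section 12. Say also from what point a patient counts as enrolled, so that the word means the same in Sections 4 and 12.
2. In Section 4, replace the target of 20 with a statement that 25 RT patients will be enrolled to yield 20 with VDP at baseline and Visit 2, matching Sections 6 and 12.
3. Reconcile the consent total. If attrition covers screen failures, so that the 25 are counted from consent, about 35 stands. If it does not, add the sponsor's own allowance for screen failures; the documents give no rate from which to derive one.

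The cost is one line in Section 4 and one clarifying sentence. No patients are added beyond Section 12's 25, and the power calculation is unchanged. The consent total rises only if screen failures fall outside attrition.

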*Incidental Findings* - Anatomic  $^1\text{H}$  MR images will not be routinely reviewed by a radiologist. However, if the technologist or study personnel note suspicious findings in the anatomic ( $^1\text{H}$ ) images at the time of MRI, images from those subjects will be reviewed by a radiologist within 10 business days for incidental findings (tumors, hernias, aneurisms, etc). Such incidental findings will be communicated to the subject's physician. Copies of images will be made available to the subject's physician upon their request.

**11. Costs to the Subject and Compensation:** There are no additional costs to the subject for the MRI examination and the subjects will be compensated after each study visit for travel/parking and time for each study visit.

**12. Data Analysis & Statistical Considerations:** The primary objective of this study is to evaluate if the pulmonary function measured by MRI will worsen after radiation therapy compared to baseline.  $^{129}\text{Xe}$  Ventilation images will be quantitatively assessed by semi-automated segmentation to determine their ventilation defect percentage (VDP). Similar metrics can be applied to  $^{129}\text{Xe}$  gas exchange images, and  $^1\text{H}$  perfusion images. Each of these images will have a corresponding defect score for exchange defect percentage (EDP), and perfusion defect percentage (PDP). Although we expect radiation therapy to exert a greater effect on gas exchange (EDP) and perfusion (PDP), the bulk of our experience to date is with the more well-established VDP metric. Thus, for the purpose of hypothesis testing and power justification, we chose VDP to be the primary endpoint for measuring the worsening pulmonary function after

radiation therapy relative to baseline. We have preliminary experience with this measurement in patients with idiopathic pulmonary fibrosis (IPF), which shares some functional similarities to radiation-induced pneumonitis. In 8 patients with IPF, we observe  $VDP=20.5\pm8.8$  compared to 10 age-matched healthy control subjects with a mean  $VDP$  of  $8.1\pm2.9$ .

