DCI review and monitoring of this protocol occurs in accordance with the NCI-approved Data and Safety Monitoring Plan. Briefly, protocol review begins with an initial review by the Cancer Protocol Committee (CPC), which assesses the ethics and safety of the protocol. Documentation of these assessments will be maintained. Formal, independent monitoring will be conducted by the DCI Monitoring Team after the first 3 subjects are enrolled, followed by annual monitoring of 1-3 subjects until the study is closed to enrollment and subjects are no longer receiving study interventions that are more than minimal risk. DCI Monitoring Team reports and additional data/safety/toxicity reports submitted by the PI will be reviewed by the Safety Oversight Committee (SOC) on an annual basis. Additional monitoring may be prompted by findings from monitoring visits, unexpected frequency of serious and/or unexpected toxicities, or other concerns. Monitoring visits may also be initiated upon request by DUHS and DCI Leadership, CPC, SOC, a sponsor, an investigator, or the IRB.

**14. Privacy, Data Storage & Confidentiality:** All consent and case report forms will be stored in a locked filing cabinet in the office of the study coordinator or principal investigator. Any other digital data (images, image analysis) will be associated only with the subject identification number and the date and time of the images. Image data will be retrieved and analyzed only by study personnel. The data is stored in a password protected, controlled access account with authentication and mandatory password change features. All CRF's will use the subject identification number as the only identifier. At the end of the study the key to the code will be destroyed.

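### Cheap improvement: VDP, the only formally tested endpoint, is segmented by study personnel with no masking of the reader to visit and no set reading order

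*Combined protocol and SAP*

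**What the plan says.** The plan is a single-arm comparison of each RT patient with his or her own baseline. On this point it says the following.

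- **Source of the endpoint (Section 12).** "Ventilation images will be quantitatively assessed by semi-automated segmentation to determine their ventilation defect percentage (VDP". The operator's part in the segmentation is not described.
- **Role of the endpoint (Section 12).** VDP carries the only formal test: "To control overall type I error, formal hypothesis testing will not be conducted for the secondary endpoints for pulmonary functions". On the power calculation: "This calculation assumes a one-sided significance level of 0.05 using a Wilcoxon Signed-Rank Test".
- **Who reads (Section 14).** "Image data will be retrieved and analyzed only by study personnel".
- **What labels the images carry (Section 14).** "Any other digital data (images, image analysis) will be associated only with the subject identification number and the date and time of the images".
- **Blinding (Section 4).** The only statement is "This will be an unblinded, open-label study enrolling patients who are scheduled to undergo thoracic radiation therapy".
- **Repeat scans without RT (Section 4).** There are none: "After consent and screening, healthy volunteers will undergo just one study visit".
- **Dose-dependence (Sections 2 and 12).** Section 2 names dose- and time-dependence as the primary study objective. Section 12 adds: "Functional metrics such as RBC:barrier ratio will be computed in isodose regions and correlation plots will be generated". It also plans repeated-measures models of dose-dependent damage, for description only.

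No section masks the reader to visit, sets a reading order, or plans a repeat-reading check.

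**The concern.** A semi-automated method leaves some room for operator judgement, though the plan does not say how much. The study team states in Section 2 that it expects function to worsen after RT, which is the direction in which a one-sided test rejects. If the person segmenting knows which scan is post-RT, small choices about defect borders or manual corrections could lean that way. Drift in technique could also enter if baseline scans are read months before follow-up scans.

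In a controlled study a shift common to both arms would largely cancel. Here it cannot: healthy volunteers are scanned once, so there is no untreated pre/post change to subtract. At stake is how convincing a positive result would be on the one formal test. A critic could say that the reader knew the visit, and nothing in the plan answers that.

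The open-label design is not an answer. Patients and staff know that RT was given, but image files can still be recoded so that the person segmenting them does not know the visit.

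**Working it through.** **Inputs, all from Section 12.** 20 evaluable pairs; SD 16 at each visit; correlation 0.2; one-sided 0.05 Wilcoxon signed-rank test; target increase of 12, read as 12 VDP percentage points; stated power about 81% from 2000 simulated samples. For sensitivity, SD 8.8, the value for the 8 IPF patients.

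**Step 1: SD of the paired change.** SD of change = SD × √(2 × (1 − correlation)).
- At SD 16: 16 × √1.6 = 20.24.
- At SD 8.8: 8.8 × √1.6 = 11.13.

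**Step 2: the test.** With 20 pairs, the exact one-sided signed-rank test at 0.05 rejects when the sum of positive ranks is at least 150. Its exact size is 0.0487.

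**Step 3: the plan's own figure.** Simulating changes as Normal(12, 20.24) gives power of about 80%, against the stated 81%. The figure is reproduced, which supports reading the target as 12 points.

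**Step 4: effect of an assumed reader shift.** Suppose RT changes nothing, but the post-RT scan of every patient is read b points higher. The measured change is then Normal(b, SD of change). The share of simulated trials that reject is the actual one-sided error:

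| Assumed shift b (VDP points) | SD 16 | SD 8.8 |
|---|---|---|
| 0 | 4.9% | 4.9% |
| 0.5 | 6.0% | 7.1% |
| 1 | 7.4% | 10.0% |
| 2 | 10.7% | 18.4% |

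Each rate comes from at least 400,000 simulated trials; separate runs agree to within about 0.2 percentage points.

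**Step 5: scale.** At SD 16 the error reaches 10% at a shift of about 1.8 points, which is 1.8/12 = 15% of the target increase. A 2-point shift is 2/8.1, about a quarter, of the healthy mean VDP in Section 12, and 2/20.5, about a tenth, of the IPF mean.

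The documents give no figure for reader error. Every value of b is an assumption, and so is its equal application to all 20 patients.

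**The case against.** The strongest reply is that no bias has been shown. The plan contains no contradiction or wrong figure here. The step from a semi-automated method to a directional shift is conjecture, and at SD 16 a shift of half a point leaves the error close to nominal. This stands: masked reading is an added safeguard, not the correction of an error.

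Second, the dose-dependence analyses offer a check, because a uniform reading shift would not be expected to follow local dose. This stands in part. Dose-dependence is central to the study, and the RBC:barrier ratio is only an example of the metrics to be mapped. But VDP is not named for the isodose work, and these analyses are descriptive.

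Third, RT changes may be visible on the images, so masking may fail for some scans. That is true; it limits the benefit without removing it.

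Two stronger readings are tempting and should be resisted:
- A reader might infer from Section 14 that the segmenter sees the scan dates. That section deals with privacy and storage. It shows that scans could be put in order, not what is on screen during segmentation.
- A reader might infer from footnote 2 to the Schedule of Events, which has key personnel accompany subjects through each visit, that segmenters attend the scans. The footnote concerns pulmonary function testing and visit logistics, and does not say who segments.

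**Conclusion.** The point holds as a low-cost improvement to the design. What is certain is the omission: the only formally tested endpoint has operator input of unstated extent, is read by study personnel without masking or a set order, and has no untreated repeat scan against which to judge a reading shift.

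What is uncertain is the size. Across assumed uniform shifts of 0.5 to 2 points, the one-sided error is about 6% to 11% at SD 16 and about 7% to 18% at SD 8.8. These figures rest on normal changes, correlation 0.2, 20 pairs and no true RT effect. If operator input is small, so is the concern.

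A reader might take the table to mean that the primary test has an inflated error rate. The documents do not support that: they give no evidence that any shift exists. The sample size and stated power are unaffected.

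**What to change.** Add to Section 12, for the VDP values used in the primary test:

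- The baseline scan and the scan from the primary post-RT visit are given a random code and stripped of subject number, date, time and visit.
- Existing study personnel segment them in random order under a fixed written procedure that states where manual correction is allowed.
- The link to visit is restored only after the values are locked.

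The same should apply to EDP and, where acquired, PDP. Preliminary unmasked reads for technical checks, or for adjusting visit timing as Section 2 foresees, may continue but should not supply the analysed values.

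The text has to name the primary post-RT visit. Section 12 powers the test at Visit 2 (10 to 14 weeks post RT) but later describes a test at 6 weeks; these statements must be reconciled first.

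**Cost.** No extra patient, scan, visit or reader. There is some file-coding work, a written procedure and possibly a second read of some scans. Analysed reads must wait until the post-RT scans in a batch exist; with several patients per batch that is longer than one patient's own follow-up. Visible post-RT change may partly unmask some scans, so the risk is reduced rather than removed.

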### CONFIDENTIAL

The information contained in this document is regarded as confidential, and may not be disclosed to another party unless such disclosure is required to initiate the study, to conduct study-related activities, or to comply with national, state, or local laws and regulations.

Written authorization from the coordinating site and sponsor is required for disclosure otherwise.

**1. Protocol Title:** Longitudinal MR Imaging of Pulmonary Function in Patients Receiving Thoracic Radiation Treatment Pro00059856

**2. Purpose of the Study:** The purpose of this study is to evaluate a comprehensive MRI-based protocol designed to image alterations in regional lung function that occur when patients receive thoracic radiation therapy. Radiation therapy (RT), when applied to tumors in or around the thorax, is known to cause regional lung injury (as defined by imaging changes reflecting reduced perfusion, reduced ventilation, and increased density) typically evolving 1-6 months post-RT. Approximately 5-20% of patients experience global lung dysfunction manifested as dyspnea after RT. This often occurs before imaging abnormalities are detected by conventional modalities (CT, SPECT). The exact linkage between the changes in imaging and the development of symptoms is unclear (for example, the time course of the two do not match exactly).

Presently, there are no well-accepted methods to predict a given patient's risk of developing dyspnea after RT, and none of the prior studies have addressed regional gas exchange (which might be considered the inherent function of the lung). Thus, there exists a considerable need to develop new methods to accurately detect and monitor radiation-induced injury, especially in the early post-RT time period when most patients develop clinical symptoms.

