**Schedule of Events**

Protocol Activities	Screening (V0) 	Study Visit (V1) 	Study Visit (V2) 	Optional Study Visit (V3) 
Informed Consent 	X			
Medical History	X	(X)		
MRI Screening Form	X	(X)	(X)	(X)
Pulmonary Function Testing 		X	X	X
Pregnancy Test 	(X)	(X)	(X)	(X)
MRI Session 		X	X	X
Subject monitoring and vital signs		X	X	X
Adverse events followup 		X	X	X
Hemoglobin (optional) Finger sensor machine	X	X	X	X

1. For most subjects, screening and study visit 1 will occur on the same day. However, these visits can be conducted separately if needed as long as it is completed before the initial RT treatment. Visit 2 will occur ten to fourteen weeks post RT. Optional Visit 3 will occur thirty-two to forty weeks post RT.
2. Pulmonary function testing will include one or more of spirometry, lung volumes, DLCO and impulse oscillometry. For healthy volunteers taking part in the technical optimization part of the study, PFTs are not required, but may be collected if desired by the study team. If some or all PFT information is already available from the patient record and deemed sufficient by study personnel, PFTs may not be collected. Pulmonary function testing will be conducted at Duke Clinical Research Unit (DCRU). Key personnel will accompany the subject from the beginning through the completion of each study visit.
3. Any female patients of child-bearing potential scheduled for radiation therapy should have a negative pregnancy test per standard of care. However, if such information is not available, or for female healthy volunteers of child bearing potential participating for technical optimization, a serum pregnancy test will be performed at screening. The test must be negative and the participant must agree to use an acceptable method of birth control for the duration of the study. Then a urine pregnancy test will be completed with a negative result before each MRI if the MRI is conducted on a different day than the screening visit or other study visits. The pregnancy test will be conducted and interpreted

by study personnel who have completed competency training from the Duke Office of Clinical Research (DOCR).

4. The MRI session will be conducted on the CAMRD research MRI scanner. Hyperpolarized  $^{129}\text{Xe}$  is produced and delivered by the study team.

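### The only formal test is set at 6 weeks after RT, when no MRI is scheduled; the design, schedule and power calculation all use Visit 2 (10–14 weeks)

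*Combined protocol and SAP*

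**What the plan says.** Section 12 makes VDP the primary endpoint and, in its closing paragraph, defines the test: the VDP "increase 6 weeks after radiation therapy compared to baseline will be tested using Wilcoxon Singed-Rank test". The same paragraph adds that "formal hypothesis testing will not be conducted for the secondary endpoints for pulmonary functions", so this is the only confirmatory test in the study.

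The other places that give a time for post-RT imaging agree with one another and not with that sentence:

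- Section 12, power paragraph: the 20 evaluable patients are those with VDP "measures at both baseline and Visit 2 (at 10-14 weeks post RT".
- Section 4: post-RT imaging is at "Visit 2 (at ten-fourteen weeks post RT) and optional visit 3 (thiry-two to forty weeks post RT".
- Schedule of Events, footnote 1: "Visit 2 will occur ten to fourteen weeks post RT", and "Optional Visit 3 will occur thirty-two to forty weeks post RT". The table marks MRI sessions at V1, V2 and optional V3 only.

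Section 2 describes regional lung injury as "typically evolving 1-6 months post-RT". It also says that the timing of the post-RT assessments will be altered in light of early results, but it sets no 6-week visit.

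**The concern.** The sentence that prespecifies the primary analysis names a time at which no patient is due to be scanned. Taken at its word, the test has no scheduled paired observations. The power statement that justifies enrolling 25 patients refers to another comparison, baseline against Visit 2.

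The primary comparison should be fixed before data are seen. There are two post-RT scans, and Section 2 allows their timing to move in response to results. If the test sentence matches neither scan, the choice of visit rests on the reader's inference. Section 2 also makes time-dependence of the RT effect part of the primary objective, so the time point is a substantive part of what is being tested.

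**Working it through.** **1. Time points side by side (weeks after RT)**

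| Source | Time point | MRI scheduled? |
|---|---|---|
| Section 12, test sentence | 6 | No |
| Section 12, power paragraph | 10–14 (Visit 2) | Yes |
| Section 4 | 10–14 (Visit 2); 32–40 (optional Visit 3) | Yes |
| Schedule of Events, footnote 1 | 10–14 (Visit 2); 32–40 (optional Visit 3) | Yes |

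The number of scheduled 6-week scans is 0. Distances from week 6:

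- to the opening of the Visit 2 window: 10 − 6 = 4 weeks
- to its close: 14 − 6 = 8 weeks
- to the opening of the Visit 3 window: 32 − 6 = 26 weeks

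In months (weeks × 12/52), week 6 is 1.4 months and Visit 2 is 2.3 to 3.2 months. Both lie inside the 1–6 month span in Section 2, over which injury is described as still evolving.

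**2. Does the stated power belong to Visit 2, and does it reproduce?**

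Inputs, all from the Section 12 power paragraph: 20 pairs, a 12% increase in VDP (read as 12 percentage points), SD 16 at each time, correlation 0.2, Wilcoxon signed-rank test, one-sided 0.05, 2000 Monte Carlo samples.

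- SD of the paired change = 16 × √(2 × (1 − 0.2)) = 16 × √1.6 = 20.24.
- Exact one-sided signed-rank test with n = 20: reject when W+ ≥ 150, actual size 4.87%.
- Simulated power with a mean change of 12: 80.0% (200,000 replicates, Monte Carlo SE 0.09 points). A separate run of 100,000 replicates gave 80.1%.
- Monte Carlo SE with the plan's 2000 samples = √(0.81 × 0.19 / 2000) = 0.0088, or about 0.9 points. The stated 81% is therefore consistent with 80.0%.
- Enrolment: 20 / (1 − 0.20) = 25, as planned.

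Reading 12% as a relative increase does not fit. On the mean VDP of 20.5 reported for idiopathic pulmonary fibrosis patients, it would be 0.12 × 20.5 = 2.46 points, with power of only about 13%.

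**3. Power at 6 weeks**

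This cannot be computed. The documents give no 6-week effect size and schedule no 6-week measurement.

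**4. After the correction**

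The power calculation is already set at Visit 2. Naming Visit 2 in the test sentence leaves 25 enrolled, 20 evaluable and about 80% power.

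**The case against.** The strongest reply is that this is a clerical slip with no practical effect. Visit 2 is the only non-optional post-RT scan. The power paragraph of the same section already names the endpoint, comparison, window, test, sidedness, significance level and sample size. A 6-week test could not be run by mistake, and Visit 3 is optional and not powered, so there is little real room to choose a favourable visit. Section 2 expects visit timing to change, which makes a leftover phrase plausible, although the documents do not say that this is what happened.

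Much of this stands: the intended visit can be recovered and no number changes. It does not remove the contradiction. The power paragraph justifies the sample size, while the test sentence specifies the analysis, and on the time point they disagree. The Section 2 remark on timing creates no 6-week visit and leaves the conflict unresolved.

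A second reply is that the 1–6 month span includes both time points and gives no course for VDP, so it does not show that the effect differs between them. That is fair. The span gives no ground for treating the two as interchangeable, but it does not measure a difference. The finding rests on the conflict in the text and does not need the biological argument.

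**Conclusion.** The concern holds and must be fixed. The study's only formal test is specified at a time with no scheduled MRI, 4 weeks before the Visit 2 window opens and 8 weeks before it closes. The stated 81% power applies to Visit 2, where it reproduces at 80.0%.

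The weight of the point comes from where the error sits, in the definition of the sole confirmatory test. Sample size and power are sound for the visit they were computed for. The textual conflict needs no assumption. The power check assumes that 12% means percentage points and uses the plan's SD and correlation as given.

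**What to change.** In the test sentence of Section 12, replace the reference to 6 weeks after RT with Visit 2 (10–14 weeks post RT). The test, the power calculation, Section 4 and the Schedule of Events will then name the same scan. The one-sided 0.05 level now appears only in the power paragraph and could usefully be restated in the same sentence.

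The cost is one phrase in an amendment, with no new patients, visits or data and no change to the power statement.
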